Multicenter double-blind placebo-controlled randomized clinical trial of efficacy and safety of Kolofort in the treatment of patients with functional dyspepsia

Phase IV

Sponsor OOO «NPF «MATERIA MEDICA HOLDING»

Protocol number MMH-KOL-003

Version date: January 19, 2017

ClinicalTrials.gov Id: NCT03119766

Protocol Summary

This document represents the protocol summary for the study on human subjects. The study will be carried out in accordance with ICH GCP, National Standard of the Russian Federation GOST 52379-2005 "Good Clinical Practice", Helsinki Declaration of World Medical Association, relevant requirements of the regulatory authorities as well as the study procedures.

Title of Study

Multicenter double-blind placebo-controlled randomized clinical study of efficacy and safety of Kolofort in the treatment of patients with functional dyspepsia.

Phase: IV

_

Sponsor: OOO «NPF «MATERIA MEDICA HOLDING», Moscow, Russia

Protocol No. MMH-KOL-003

Objective of the study

 To obtain additional data on efficacy and safety of Kolofort in the treatment of patients with functional dyspepsia.

Endpoints

Primary endpoint

1. Changes in severity of functional dyspepsia (FD) symptoms on the GIS (Gastrointestinal symptom score) after 8 weeks from the start of the study therapy.

Secondary endpoints

- 1. Percentage of patients with a decrease in the severity of FD symptoms on the GIS scale after 8 weeks from the start of the study therapy.
- 2. Change in the severity of the functional dyspepsia index NDI after 8 weeks from the start of the study therapy.
- 3. Changes in the quality of life of patients on the SF-36 scale after 8 weeks from the start of study therapy.
- 4. Percentage of patients terminating the study early due to lack of efficacy of the study therapy. 1
- 5. Indicators of therapeutic and side effects values, efficacy index according to Clinical Global Impression (CGI-EI) scores after 8 weeks of treatment.

CONFIDENTIAL Page 2 of 13

¹ Lack of efficacy of the study therapy is defined as retention or progression of the symptoms of functional dyspepsia resulting in prescription of the products for FD therapy (proton pump inhibitors, prokinetics, spasmolytics).

Safety assessment

- Occurrence and nature of adverse events (AE) during the treatment; AE severity, causal relationship to the study drug, and outcome.
- Changes in vital signs.

Study design

A multicenter double-blind placebo-controlled randomized clinical trial was planned to evaluate the efficacy and safety of the study treatment.

The study will enroll the patients of either gender aged 18-45 years old with verified diagnosis of "functional dyspepsia" according to Rome-IV criteria and intensity of dyspeptic symptoms ≥ 6 according to GIS (Gastrointestinal symptom score).

At the screening visit 1 (Visit 1, from -14 to -1 days), after signing patient information sheet (informed consent form) to participate in the clinical trial, complaints and medical history are collected, an objective examination is performed. The investigator evaluates intensity of dyspeptic symptoms according to GIS. The patient undergoes an abdomen ultrasound examination, esophagogastroduodenoscopy (EGDS)², and diagnostic tests for Helicobacter pylori (H. pylori) infection. In case of the previous use of proton pump inhibitors, prokinetics, antispasmodics, antacids, bismuth drugs the investigator evaluates the possibility of canceling these drugs at least 7 days before the patient is randomized. For women of reproductive age, a pregnancy test is performed.

On the day of randomization (Visit 2, Day 0) collection of complaints and objective examination are carried out. The investigator evaluates the results of laboratory and instrumental research methods, the severity of dyspepsia symptoms on the GIS scale, registers changes in concomitant therapy.

If a patient meets all inclusion criteria and does not have any exclusion criteria, he/she is randomized into one of two groups: Patients in Group 1 receive Kolofort for 8 weeks; Patients in Group 2 – Placebo on the study drug regimen. The patient completes the Nepean Dyspepsia Index (NDI) and Quality of Life (SF-36) questionnaires.

The patient's treatment lasts for 8 weeks, during which 3 visits to the research center are carried out. At Visit 3 (Week 2 ± 3 days), complaints are collected, an objective examination of the patient is performed. The investigator monitors the prescribed and concomitant therapy, evaluates the safety of the therapy and the degree of adherence to treatment (compliance). At visit 4 (week 4 ± 3

CONFIDENTIAL Page 3 of 13

² It is possible to use the results of an EGDS performed earlier in any medical facility, provided that the procedure was carried out no more than one month ago from the screening visit and that the patient has a corresponding video recording and conclusion.

days) and 5 (week 8±3 days) the investigator collects complaints, registers the physical examination data, monitors the prescribed and concomitant therapy, assesses the safety of the treatment and compliance. Questionnaires GIS, NDI are filled in.

Additionally, at Visit 5 the patient fills out the SF-36 scale, the investigator fills out the Clinical Global Impression-Efficacy Index (CGI-EI).

The patients will be allowed to take symptomatic therapy and medications for their co-morbidities during the study, except for the medicines listed in "Prohibited Concomitant Treatment".

Inclusion and exclusion criteria

Inclusion criteria

- 1. Patients of both genders aged 18-45 years old.
- 2. Diagnosis of functional dyspepsia established according to Rome-IV criteria (2016).
- 3. Severity of symptoms of dyspepsia ≥ 6 on the GIS scale.
- 4. Negative test result for H. pylori infection³.
- 5. Availability of signed patient information sheet and informed consent form for participation in the clinical trial.
- 6. Patients who gave their consent to use reliable contraception during the study.

Exclusion criteria

- 1. Organic diseases of the gastrointestinal tract (gastroesophageal reflux disease (GERD), peptic ulcer, chronic pancreatitis, cholelithiasis, hepatosis, hepatitis, hepatic cirrhosis, etc.)⁴
- 2. Verified diagnosis of other functional GI diseases, i.e. biliary dyskinesia, irritable bowel syndrome, etc.
- 3. Discontinuation of proton pump inhibitors, prokinetics, antispasmodics, antacids, bismuth preparations less than 7 days before randomization.
- 4. H. pylori eradication within 2 months prior to enrollment.
- 5. Intestinal infection within 2 months prior to enrollment.
- 6. History/suspicion of oncology of any location.
- 7. Previously diagnosed cardiovascular diseases with functional class IV (according to the classification of the New-York Heart Association, 1964), hypothyroidism, diabetes mellitus, chronic renal disease C3-5, hepatic diseases with portal hypertension and/or signs of severe decompensation of function (> 6 points according to the Child-Pugh classification).

CONFIDENTIAL Page 4 of 13

_

³ Biopsy express test and/or fecal antigen and/or breath test.

⁴ Enrollment of subjects with morphological signs of chronic gastritis without signs of atrophy, metaplasia, hemorrhages, erosions and ulcerative lesions of mucosa is allowed.

- 8. Any other severe comorbidity that, in the opinion of the investigator, may affect patient participation in the clinical trial.
- 9. Allergy/intolerance intolerances to any of the components of the study drugs.
- 10. Pregnancy, breast-feeding.
- 11. Patients who, from the investigator's point of view, will not comply with the observation requirements of the study or adhere to study drug dosing regimens.
- 12. Scheduled hospitalization during the study for any diagnostic or therapeutic procedures.
- 13. Use of drugs or alcohol (more than 2 alcohol units daily), presence of mental diseases.
- 14. Use of any medications specified in the "Prohibited Concomitant Treatment" within 1 month prior to inclusion in the study.
- 15. Participation in other clinical trials in the previous 3 months.
- 16. Patients who are related to any of the on-site research personnel directly involved in the conduct of the trial or are an immediate relative of the study investigator. 'Immediate relative' means husband, wife, parent, son, daughter, brother, or sister (regardless of whether they are natural or adopted).
- 17. Patients who work for MATERIA MEDICA HOLDING (i.e. the company's employees, temporary contract workers, appointed officials responsible for carrying out the research or immediate relatives of the aforementioned).

Criteria for Withdrawal or Termination

- 1. Screening failure.
- 2. Lack of study therapy efficacy⁵.
- 3. Inability or refusal of patient to comply with the protocol requirements.
- 4. Necessity in medicines prohibited within the study.
- 5. An adverse event requiring cancellation of the study drug.
- 6. Incorrect inclusion of ineligible patient.
- 7. Pregnancy.
- 8. Desire of patient to complete the study ahead of schedule due to any reason.
- 9. Cases not specified by the protocol where the investigator decides that further participation may harm the patient.

Number of subjects

It is planned to enroll 370 subjects, among those at least 258 patients are expected to complete all procedures of the protocol (129 patients each in the Kolofort and Placebo groups).

CONFIDENTIAL Page 5 of 13

-

⁵ Lack of efficacy of the study therapy is defined as retention or progression of the symptoms of functional dyspepsia resulting in prescription of the products for FD therapy (proton pump inhibitors, prokinetics, antispasmodics).

Interim analysis

A blinded interim analysis is planned in order to specify the study parameters As a result of an interim analysis, it is possible to change the sample size, but only upward.

Treatment

Group 1

Name of the medicinal product: Kolofort

Active ingredient: affinity purified antibodies to human TNF α – 0.006 g*

Affinity purified antibodies to S100 brain-specific protein – 0.006 g*

Affinity purified antibodies to histamine – 0,006 g*

* applied onto lactose monohydrate as a mixture of three active aqueous-alcoholic dilutions of the substance diluted 100^{12} , 100^{20} , 100^{200} times, respectively

Excipients: lactose monohydrate, microcrystalline cellulose, magnesium stearate

Method of administration: Tablet for oral use. Dose per administration: 2 tablets. 2 tablets twice daily (4 tablets per day). The tablets should be held in the mouth until complete dissolution, without meal

Dosage form: Tablets

Description: Flat cylinder-shaped scored bevelled edge white to off-white tablets

Storage conditions: Store protected from light at temperature below 25°C. Keep out of the reach of children.

Group 2

Name of the medicinal product: Placebo

Active ingredient: NA

Excipients: lactose monohydrate, microcrystalline cellulose, magnesium stearate

Method of administration: Tablet for oral use. Dose per administration: 2 tablets. 2 tablets twice daily (4 tablets per day). The tablets should be held in the mouth until complete dissolution, without meal.

Dosage form: Tablets.

Description: Flat cylinder-shaped scored bevelled edge white to off-white tablets

Storage conditions: Store protected from light at temperature below 25°C. Keep out of the reach of children.

Treatment duration

Kolofort/Placebo treatment duration is 8 weeks.

CONFIDENTIAL Page 6 of 13

Observation period

In total the patients will be monitored for 10 weeks (screening, randomization up to 2 weeks, treatment - 8 weeks).

Symptomatic (Standard) treatment

Patients are allowed to receive medications used to treat the underlying and concomitant diseases other than those representing exclusion criteria, except for the drugs specified in the section "Prohibited concomitant treatment".

Prohibited concomitant therapy

[figure not shown]
Within 1 month prior to enrollment and throughout the study (after signing information sheet (informed consent form) and screening onset) the patients are not allowed to use any of the following medications (ATC group is specified in brackets):

- 1. Preparations used for conditions associated with acidity disorders (A02)
- 2. Preparations for treatment of functional gastrointestinal disorders (A03)⁶
- 3. Fenspiride (R03DX03)
- 4. Antihistamines (R06)
- 5. Steroidal and non-steroidal anti-inflammatory preparations (except for topical/inhalation corticosteroids)
- 6. Anti-inflammatory and antirheumatic preparations (M01) and analgesics (N02)
- 7. Antineoplastic preparations (L01) and antineoplastic hormones (L02)
- 8. Immunostimulants (L03)
- 9. Immunosuppressants (L04)
- 10. Immune sera and immunoglobulins (J06)
- 11. Vaccines (J07)
- 12. Preparations of calcium, iron, zinc, potassium
- 13. Antibacterials for systemic use (J01)
- 14. Proproten, Tenoten, Brizantin, Divaza, Ergoferon, Arthrofon, Rengalin, Prohistam
- 15. Homeopathic drug products
- 16. Preparations the use of which the patient has previously had allergic reactions.

Study design scheme

CONFIDENTIAL Page 7 of 13

⁶ Administration of a spasmolytic agent drotaverine by the subject is allowed at the total dose of no more than 640 mg (equivalent to 16 drotaverine tablets 40 mg or 8 drotaverine tablets 80 mg) throughout the study period.

Schedule of study procedures

Procedure/Visit	Screening	Randomization	Treatment Administration of Kolofort/Placebo		on of
	Visit 1	Visit 2	Visit 3	Visit 4	Visit 5
	From		Week	Week	Week
	day –14	Day 0	2±3	4 ± 3	8± 3
	to day -1		days	days	days
Informed consent	+				
Collection of complaints	+	+	+	+	+
Medical history	+				
Concomitant conditions and diseases	+	+			
Physical examination	+	+	+	+	+
Completing the GIS scale	+	+		+	+
Abdominal ultrasound	+				
EGDS	+				
H. pylori test	+				
Concomitant therapy	+	+	+	+	+
Necessity in concomitant therapy (for dyspepsia therapy)			+	+	
Pregnancy test	+				
Inclusion/exclusion criteria	+	+			
Randomization, prescription of the study therapy		+			
Completing the NDI Questionnaire		+		+	+
Evaluation of quality of life according to SF-36 scale		+			+
Study drug supply		+	+	+	

CONFIDENTIAL Page 8 of 13

Study drug accountability and return, compliance assessment		+	+	+
Clinical Global Impression assessment (CGI-EI)				+
Evaluation of treatment safety	+	+	+	+

Statistical Analyses

Samples

Total set includes all the patients who have signed ICF. This sample will consider all adverse events throughout the study.

The sample including all subjects who received at least one dose of the study product to be used for *analysis of the study treatment safety and tolerability* (*Safety population*), as all adverse events identified after the study product administration will be recorded.

Full Analysis Set This sample will consist of all enrolled subjects, except for those who met at least one of the following criteria:

- 1) noncompliance with inclusion/non-inclusion criteria;
- 2) patient has not taken any dose of the study drug;
- 3) lack of any data on the patient after randomization.

This is the most appropriate set for the Intention-to-treat principle, so it will be used in the *Intention-to-treat analysis (ITT-analysis) of efficacy of the study therapy.*

Per Protocol set. This sample includes all patients who completed the therapy as per the study protocol, without any missing visits or major protocol deviations. This set will be used for Per Protocol analysis (PP analysis) of efficacy of the study therapy.

Mean value of the total set for the relevant day will be used to fill lacking/missing data.

Data treatment and all statistical calculations under the protocol will be carried out using SAS-9.4 statistical software.⁷

Evaluation of sample size

The sample size was assessed in accordance with the following rules and assumptions:

- 1. Statistical assumptions:
 - 1.1 the power of statistical tests " $P=(1-\beta)$ " will be taken as being equal to 80% (the probability of correct rejection of the null hypothesis is 0.8)
 - 1.2 the probability of type 1 error ' α ' is less than 5% (the probability of false acceptance of the alternative hypothesis is less than 0.05)
 - 1.3 statistical criteria of intergroup comparisons used are two-sided

CONFIDENTIAL Page 9 of 13

-

⁷ Holder of license: OOO "NPF "MATERIA MEDICA HOLDING", No. 70100045.

- 1.4 calculation of sample size is based on the assumptions on the expected effect declared in the primary efficacy criterion of the protocol
- 1.5 ratio between Kolofort and Placebo sample sizes is 1:1 (1 Kolofort subject per 1 Placebo subject)
- 1.6 statistical null and alternative hypotheses will be as follows:

$$H_0$$
: $\Delta \mu_{\kappa} = \Delta \mu_{\Pi}$

$$H_a$$
: $\Delta \mu_{\kappa} \neq \Delta \mu_{\Pi}$,

where $\Delta \mu_{K}$ - mean reduction (baseline – final score) total GIS score in Kolofort group

 $\Delta \mu_{II}$ – mean reduction (baseline - final score) of total GIS score in Placebo group

1.7 calculation of sample size will be made using the following formula:

$$n_1 = n_2 = \frac{2(z_{\alpha/2} + z_{\beta})^2 \sigma^2}{\epsilon^2}$$

where n_1 and n_2 are sample sizes in study drug and placebo groups, respectively

- ε expected difference in mean reduction of total score between Kolofort and Placebo groups
- σ standard deviation of reduction in total score (assessed based on bibliographic data)

 $z_{\alpha/2}$ – tabular value of two-sided z-test for α

 z_{β} – tabular value of one-sided z-test for β

1.8 final sample size will be determined using the formula:

$$N_T = N_{PP} / (1 - K_B),$$

where N_T – final sample size;

 N_{PP} – result of calculation in cl. 1.7, i.e. scheduled number of patients completing the study per protocol

 $\mathbf{K}_{\mathbf{B}}$ – withdrawal coefficient.

- 2. Assumptions on expected clinical study effects:
 - 2.1 The difference between reduction ("total score at baseline visit" "total score at final visit") in total GIS score in Kolofort and Placebo groups will be at least 15% from baseline value (d=0.15, calculated as the difference between group values of GIS reduction attributed to mean starting value).
 - 2.2 The values of population variance of reduction in total GIS score and baseline mean total score were evaluated based on bibliographic review as follows:

 $\varepsilon = d^*(E - z(_{1-\alpha/2})^*S_0/n^{0,5})$ is the lower limit of confidence interval for mean total GIS score for placebo group in the relevant study (conservative estimate)

CONFIDENTIAL Page 10 of 13

d=0.15 – claimed effect size

E=12 – mean starting GIS score based on the source cited

 S_0 =4.7 – sample standard deviation at the first visit in Placebo group based on the source cited

6=S*((n-1)/χ²_{α/2,(n-1)})^{0,5} is the upper limit of 95% confidence interval for population standard deviation of total score reduction (conservative estimate)

where S is sample standard deviation for the reduction in total GIST score between the first and last visits based on the source cited

S=4.3

n=157

 $\chi^2_{\alpha/2,(n-1)}$ is the corresponding quintile of chi-square distribution

$$\chi^{2}_{0.025, 156} = 123.3$$

therefore, effect size and standard deviation estimates are equal to

$$\varepsilon$$
=0.15*(12-1.96*4.7/12.52) = 1.69
 ε =4.3*(156/123.3)^{0.5} = 4.84.

Therefore, the sample size has been found to be **129** patients in each of the groups (Kolofort and Placebo) to estimate superiority of the study drug over placebo.

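### Because any GIS decrease counts as response, filling missing Week 8 scores with the overall mean can turn most withdrawn patients into responders, including those who stopped for lack of efficacy

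*Combined protocol and SAP*

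**What the plan says.** In the Endpoints list, the first secondary endpoint is the "Percentage of patients with a decrease in the severity of FD symptoms on the GIS scale after 8 weeks" from the start of therapy. Neither that list nor the Statistical Analyses section gives a number of points, a percentage or a cut-off, so read literally a one-point fall is a response. Secondary endpoint 4 is the percentage who leave early for lack of efficacy. Its footnote defines this as persisting or worsening symptoms that lead to other dyspepsia drugs being prescribed.

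Under Statistical Analyses, Samples, the only missing-data rule is: "Mean value of the total set for the relevant day will be used to fill lacking/missing data". It makes no exception for responder endpoints or by reason for withdrawal, and does not say whether the score is filled before response is derived. The Full Analysis Set keeps treated, eligible patients with any data after randomization. The Per Protocol set excludes patients with missed visits.

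Inclusion criterion 3 requires "Severity of symptoms of dyspepsia ≥ 6 on the GIS scale". Evaluation of sample size uses a mean starting GIS of 12, a baseline SD of 4.7 and 30% withdrawal. Number of subjects expects at least 258 completers out of 370.

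**The concern.** The two rules interact badly. A pooled mean sits in the middle of the Week 8 distribution. If patients improve on average, it lies below most baselines, so almost any improvement in the overall mean creates a decrease for many patients who were never measured at Week 8. The responder status assigned to them reflects their own baseline and other patients' outcomes, not their own course.

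Patients who stopped because treatment did not work are the clearest case. The plan calls them failures in one secondary endpoint and, in the Full Analysis Set, would usually call them responders in another. An arm that loses more patients to lack of efficacy would not be marked down for it on endpoint 1.

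**Working it through.** **The plan's own figure.** No response rate or power is stated for this endpoint. The nearest figure is the primary sample size: 2 × (1.96 + 0.8416)² × 4.84² / 1.69² = 128.75, so 129 per arm. Then 129 / 0.70 = 184.3, so 185 per arm and 370 in total. Both reproduce.

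**Inputs.** Baseline mean 12 and SD 4.7 (Evaluation of sample size); entry at GIS 6 or more (inclusion criterion 3); 30% withdrawal (Evaluation of sample size). Assumptions not in the documents: a normal baseline cut at 6, withdrawn patients with the same baseline distribution as the rest, and an overall Week 8 mean c of 11, 9 or 7.

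**Formula.** A filled patient is a responder if baseline exceeds c. With whole-number scores and whole-number c, that means baseline of at least c + 1. The share is P(B ≥ c + 1) / P(B ≥ 6) for B ~ N(12, 4.7), calculated without and with a half-point continuity correction.

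| Week 8 mean c | No correction | Half-point correction |
|---|---|---|
| 11 | 0.500 / 0.899 = 56% | 0.542 / 0.917 = 59% |
| 9 | 0.665 / 0.899 = 74% | 0.703 / 0.917 = 77% |
| 7 | 0.803 / 0.899 = 89% | 0.831 / 0.917 = 91% |

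**Sensitivity to baseline shape.** Suppose instead that 12 and 4.7 describe the population after the cut at 6. The underlying normal then has mean 3.90 and SD 8.41, and P(B > c) / P(B > 6) is 0.199 / 0.401 = 50% at c = 11, 0.272 / 0.401 = 68% at c = 9 and 0.356 / 0.401 = 89% at c = 7. At a Week 8 mean of 11, then, the share is only about half. It is a clear majority at 9 and below under either reading.

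**Effect on the Full Analysis Set rate.** If 30% of each arm is filled, those patients add 0.30 × 56-59% = 17-18 percentage points to the response rate at c = 11, 0.30 × 74-77% = 22-23 at c = 9 and 0.30 × 89-91% = 27 at c = 7. If they counted as non-responders they would add none. The 30% is an upper bound: it is set against patients signing consent, and screening failure is listed among the withdrawal criteria, so fewer may be filled.

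**The case against.** The best defence has four parts, and each partly stands.

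- **Order of fill.** The plan does not say that response is derived from filled scores. True, but no other handling is given, so the rule as written leads there.
- **Other analyses.** The Per Protocol set excludes missed visits, and endpoint 4 counts lack-of-efficacy failures openly. Neither corrects endpoint 1 in the Full Analysis Set.
- **A general defect.** Mean fill affects other endpoints too. True, but only here does it turn a known failure into a success.
- **Equal withdrawal.** If both arms lose the same share for the same reasons, mean fill and a non-responder rule give the same difference between arms. The level is still wrong, and with unequal withdrawal so is the difference.

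A reader might also infer stronger things that the documents do not support.

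- **That 70-91% of placebo patients respond.** With the plan's SD of 4.84 and a threshold of 0.5 points, the placebo rate is Φ((m − 0.5) / 4.84) for a mean placebo reduction m: 70%, 82% and 91% at m = 3, 5 and 7, but 46%, 54% and 62% at m = 0, 1 and 2. The plan states no placebo reduction.
- **That low power is an error.** The 80% power is for the primary mean change; none is promised here. Nor does a 50% cut-off reliably help. At 129 per arm and SD 4.84, with no placebo improvement, any decrease has about 60% power against 46% for a fixed 5.5-point cut. The 50% rule gains only at larger placebo reductions.
- **That this is the only patient-level endpoint.** Endpoints 4 and 5 are also patient-level.
- **That the sample-size effect implies a cut-off.** The difference that "will be at least 15% from baseline value" is between group means; it sets no individual response.

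**Conclusion.** The concern holds as an interaction between a threshold-free responder definition and the pooled-mean fill. Followed as written, with the score filled and response then derived, the plan would class about 56-59%, 74-77% or 89-91% of withdrawn patients as responders at an overall Week 8 mean of 11, 9 or 7. The result rests on that order of derivation, on an assumed Week 8 mean, and on withdrawn patients having typical baselines. The lowest case also depends on baseline shape and could be nearer half. The number of lack-of-efficacy withdrawals is not given, so their contribution cannot be isolated. The contradiction with endpoint 4 needs no numerical assumption beyond a baseline above the fill value.

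This is a secondary endpoint and the correction is small. The lack of a threshold is a weakness of interpretation, since small fluctuations count as benefit, but not an arithmetical error.

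**What to change.** In the SAP, for secondary endpoint 1:

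1. State that the mean fill is not applied.
2. Count patients who stop for lack of efficacy, or who start prohibited dyspepsia therapy, as non-responders. Say how the drotaverine use permitted under Prohibited concomitant therapy is classified.
3. Preferably count every other withdrawal without a Week 8 score as a non-responder too, and give a sensitivity analysis under a different assumption for those patients.

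Optionally, report by arm the cumulative distribution of percentage GIS reduction from Visit 2, or a response threshold fixed before unblinding, and keep any decrease as a descriptive line. A figure such as 50% would be a reviewer's choice; nothing in the documents supports it, and it should not be justified on power.

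The cost is wording only: GIS is already collected at Visits 2, 4 and 5, and reasons for withdrawal are needed for endpoint 4. The downside is a lower response rate in both arms.

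### In the Per Protocol analysis, secondary endpoint 4 (early termination for lack of efficacy) is 0% in both arms by construction, and the plan does not restrict it to the FAS

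*Combined protocol and SAP*

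**What the plan says.** Under Statistical Analyses, Samples, the PP set is defined thus: "This sample includes all patients who completed the therapy as per the study protocol, without any missing visits or major protocol deviations". Its use follows: "This set will be used for Per Protocol analysis (PP analysis) of efficacy of the study therapy". No endpoint is exempted.

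Secondary endpoint 4 is "Percentage of patients terminating the study early due to lack of efficacy of the study therapy". Its footnote, repeated under Criteria for Withdrawal or Termination, defines lack of efficacy as "retention or progression of the symptoms of functional dyspepsia resulting in prescription of the products for FD therapy". Criterion 2 of that list, "Lack of study therapy efficacy", takes such a patient out of the study.

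Of the FAS the plan writes "This is the most appropriate set for the Intention-to-treat principle, so it will be used in the" intention-to-treat analysis of efficacy. The FAS excludes patients who breach the entry criteria, take no dose, or have no data after randomisation. Early termination is not an exclusion. Missing values are filled with the total-set mean for the day concerned. Nothing says whether the FAS or the PP result is primary.

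Evaluation of sample size, item 1.8, inflates from N_PP, described as the "scheduled number of patients completing the study per protocol".

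**The concern.** Endpoint 4 is an event of non-completion, and the PP set admits completers only. If every efficacy endpoint is run in both sets, as the text allows, the PP table for endpoint 4 is empty of events in both arms. It carries no information on the drug, and a reader who does not go back to the set definition may take it as an absence of treatment failures.

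The same patients are missing from the PP responder rate for endpoint 1. They are also missing from the PP comparison of GIS change, so membership of that set depends partly on response.

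**Working it through.** **1. The plan's own figures.** Inputs from Evaluation of sample size: ε = 1.69, σ = 4.84, two-sided α = 0.05, power 80%.

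n = 2(1.96 + 0.8416)² × 4.84² / 1.69² = 128.8, so 129 per arm, as stated. Then 129 / (1 − 0.30) = 184.3, so 185 per arm and 370 in total, as stated. The plan expects at least 258 to complete, so up to 370 − 258 = 112 may fall outside the PP set. That covers all reasons, and how many would be efficacy failures is not stated.

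**2. Endpoint 4 by set membership.**
- An endpoint-4 event means leaving the study early under withdrawal criterion 2.
- Leaving early means therapy was not completed and Visit 5 was not made.
- PP membership requires completion and no missed visit.

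No patient can satisfy both. The PP result is 0/n versus 0/n (Fisher p = 1) at any true rates.

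In the FAS the endpoint can be estimated. The rates below are assumptions, and 185 per arm in the FAS is an upper limit:

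| Assumed failure rate, Kolofort vs placebo | FAS events | Fisher p | PP events |
|---|---|---|---|
| 2% vs 5% | 4/185 vs 9/185 | 0.26 | 0 vs 0 |
| 5% vs 15% | 9/185 vs 28/185 | 0.0015 | 0 vs 0 |
| 10% vs 20% | 18/185 vs 37/185 | 0.008 | 0 vs 0 |

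**3. Endpoint 1.** If a proportion q of an arm stops for lack of efficacy and r is the responder rate among the rest, PP reports r. Counting failures as non-responders gives r(1 − q). At q = 10% vs 20%, the PP rates would be multiplied by 0.90 and 0.80.

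**4. GIS, illustration only.** Assume normal reductions with SD 4.84 and a true difference of 1.69. Withdrawal occurs below a common cut-off on a score that correlates ρ with the week-8 reduction within each arm. Put δ = 1.69/4.84 = 0.349 and let w be the overall withdrawal rate.

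- Cut-off c solves [Φ(c) + Φ(c − ρδ)]/2 = w, with q_P = Φ(c) and q_K = Φ(c − ρδ).
- Completers' means, with the placebo mean set at 0: m_P = 4.84ρφ(c)/(1 − q_P) and m_K = 1.69 + 4.84ρφ(c − ρδ)/(1 − q_K).
- PP difference = m_K − m_P.
- FAS difference with failures filled by the pooled completers' mean M = (1 − q_K)(m_K − M) − (1 − q_P)(m_P − M).

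Example, ρ = 0.7 and w = 10%: c = −1.169, q_P = 12.1%, q_K = 7.9%, m_P = 0.777, m_K = 2.230, M = 1.521. PP = 1.45. FAS = 0.921 × 0.709 + 0.879 × 0.744 = 1.31.

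| Withdrawn | ρ | PP difference (shrinkage from 1.69) | FAS difference, mean-imputed |
|---|---|---|---|
| 10% | 0.5 | 1.57 (7%) | 1.41 |
| 10% | 0.7 | 1.45 (14%) | 1.31 |
| 20% | 0.5 | 1.51 (10%) | 1.21 |
| 20% | 0.7 | 1.35 (20%) | 1.08 |
| 10% | 1 (exact cut) | 1.21 (28%) | 1.09 |
| 20% | 1 (exact cut) | 0.99 (41%) | 0.79 |

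In every row the mean-imputed FAS lies further from 1.69 than PP does.

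**5. Direction.** Take a different model: completers' mean reductions of 7.69 and 6.00, and failures improving by f = 0 to 2 points. PP shows 1.69 throughout. With failures included:
- 15% failing in each arm: 0.85 × 1.69 = 1.44, so PP is too large.
- 10% vs 20% failing: 0.9 × 7.69 − 0.8 × 6.00 − 0.1f = 2.12 − 0.1f, that is 1.92 to 2.12, so PP is too small.

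**The case against.** The strongest reply is that a set of completers without major deviations is an ordinary PP definition. Patients who stop for lack of efficacy do so because FD drugs were prescribed. Those drugs are largely on the prohibited list, and needing a prohibited medicine is a separate withdrawal criterion. Leaving these patients out of a PP set is therefore defensible. That stands, and the point is not an objection to the PP definition itself. What remains is that an endpoint defined by non-completion is not exempted from an analysis of completers.

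Stronger readings that a reader might infer, and why the documents do not support them:
- *Endpoint 4 cannot be evaluated in this trial.* It can, in the FAS.
- *PP is the deciding analysis because the trial is sized on N_PP.* Item 1.8 is routine inflation for dropout and does not rank the sets. The sets are indeed unranked in this text, but the document calls itself a protocol summary, so that silence is weaker evidence than it would be in a full SAP.
- *PP removes the worst responders and shrinks the GIS difference by 28–41%.* Those figures need an exact cut on the week-8 change at assumed withdrawal rates. The plan defines failure by prescription of FD drugs, and patients who stay symptomatic but finish remain in the PP set.
- *Making the FAS primary repairs the GIS comparison.* Under the plan's mean imputation it does not, as step 4 shows.

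**Conclusion.** The concern holds for endpoint 4 and, by the same logic, for the PP responder rate. The 0% versus 0% follows from the plan's definitions alone and needs no assumption about rates. It affects one of five secondary endpoints in one of the two efficacy analyses, and the FAS still captures the endpoint.

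For GIS the size is not established. Shrinkage of about 7–20% rests on assumed withdrawal of 10–20% and an assumed correlation of 0.5–0.7, and its sign depends on the model. The imputation result assumes that the week-8 total-set mean is the mean over completers of both arms.

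**What to change.** In Statistical Analyses, Samples, before unblinding:

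1. State that secondary endpoint 4 is analysed in the FAS only, with all FAS patients in the denominator.
2. State that patients who terminate early for lack of efficacy count as non-responders for secondary endpoint 1 in the FAS.
3. State that the FAS analysis is primary and PP supportive, but only together with item 4.
4. For patients who stop for lack of efficacy, replace the total-set mean imputation of GIS with a pre-specified rule that does not score them as average (for example, no improvement from baseline), with a sensitivity analysis under a second rule.

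No extra data, visits or patients are needed. The cost is one fewer PP table, a slightly less favourable responder rate, and the work of specifying item 4.
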